AUC _{0-28d_{ss}}	AUC between doses at steady state where dosing interval (τ) = 28 days (4 weeks)
AUC _{0-τ}	Area under the concentration-time curve in a dosing interval
AUC _{0-∞}	AUC from time 0 to infinity
BP	Blood pressure
BNP	B-type natriuretic peptide
CI	Confidence interval
CKD	Chronic kidney disease
CKD-EPI	Chronic Kidney Disease Epidemiology Collaboration
C _{max}	Maximum concentration
COVID-19	Novel coronavirus 2019
CSL	CSL Behring LLC
cTnI	Cardiac troponin-I
CTRA	Clinical Trial Research Agreement
C _{trough}	Trough concentration
C _{trough_{ss}}	Trough concentrations at steady state
CV	Coefficient of variation (%)
DBP	Diastolic blood pressure
DKD	Diabetic kidney disease
EC ₅₀	Half maximal effective concentration
ECG	Electrocardiogram
ECHO	Echocardiogram

Abbreviation	Term
eCRF	Electronic case report form
eGFR	Estimated glomerular filtration rate
EOS	End of study
FCBP	Female subjects of childbearing potential
FDA	Food and Drug Administration
FMV	First morning void
GCP	Good Clinical Practice
HbA1c	Hemoglobin A1c
HBsAg	hepatitis B surface antigen
HBV	Hepatitis B virus
HDL	High density lipoproteins
HFD	High-fat diet (mouse model)
ICF	Informed consent form
ICH	International Council for Harmonisation of Technical Requirements for Pharmaceuticals for Human Use
IDMC	Independent Data Monitoring Committee
IEC	Independent Ethics Committee
IgG	Immunoglobulin G
IMP	Investigational Medicinal Product (Handing Manual)
IP	Investigational product
IRB	Institutional Review Board
IRT	Interactive response technology
ITT	Intention-to-Treat
IV	Intravenous
LVEF	Left ventricular ejection fraction
MMRM	Mixed effects model, repeated measures
NEFA	Non-esterified fatty acids
PD	Pharmacodynamic
PK	Pharmacokinetic
RAS	Renin angiotensin system
SAE	Serious adverse event
SAP	Statistical analysis plan

Abbreviation	Term
SBP	Systolic blood pressure
SC	Subcutaneous
SCr	Serum creatinine
SD	Standard deviation
SGLT2	Sodium-glucose cotransporter 2
SOC	Standard of care
T2DM	Type 2 diabetes mellitus
T _{max}	Time to reach maximum concentration in serum
ULN	Upper limit of normal
URL	Upper reference limit
VEGF	Vascular endothelial growth factor

1 Introduction

1.1 Background

Diabetic kidney disease (DKD) is the most common cause of end stage renal disease and its prevalence continues to grow worldwide [GBD 2018]. Diabetic kidney disease is first detected by the abnormal loss of small amounts of albumin into the urine (microalbuminuria). As DKD progresses with increasingly larger losses of urinary albumin, renal function declines leading to chronic kidney disease (CKD) and the eventual initiation of renal replacement therapy. The standard of care (SOC) to slow the decline in renal function in patients with DKD has consisted of glycemic control, use of renin angiotensin system (RAS) inhibitors, and management of hypertension and hyperlipidemia [KDOQI, 2007 and 2012]. The SOC is expected to evolve over the next few years to include the use of sodium-glucose cotransporter 2 (SGLT2) inhibitors [Perkovic et al, 2019; Sarafidis et al, 2019; Garber et al, 2019]. Nevertheless, treatment with both RAS and SGLT2 inhibitors does not arrest or reverse the progression of DKD [Khan and Quaggin, 2015; Perkovic et al, 2019]. Worldwide, over 300,000 patients with DKD progress to end stage kidney disease requiring dialysis or renal transplant each year. Thus, additional treatment options are needed to preserve renal function.

Vascular endothelial growth factor (VEGF)-B primarily regulates fatty acid transport across the endothelium [Hagberg et al, 2010], whereas other members of the VEGF family stimulate de novo growth of blood vessels (ie, angiogenesis; VEGF-A and placental growth factor, to a lesser extent) or lymphatic vessels (ie, lymphangiogenesis; VEGF-C and -D). In DKD, VEGF-B expression in the diabetic kidney (murine and human) is elevated and associated with increased lipid deposition in glomerular podocytes as free fatty acids are shunted from adipose tissue (murine) [Falkevall et al, 2017]. The DKD phenotype is observed in podocyte-specific VEGF-B overexpressing mice [Falkevall et al, 2017]. Reducing VEGF-B activity in mouse models of type 1 diabetes mellitus (streptozotocin-induced diabetes) and type 2 diabetes mellitus (T2DM, *db/db*, or high-fat diet [HFD]-induced)-DKD with an anti-VEGF-B antibody results in improvement of histological evidence of glomerular injury and reduces albuminuria [Falkevall et al, 2017]. The beneficial effects of blocking VEGF-B activity have been attributed to the prevention of toxic lipid accumulation in the kidney. A molecule that antagonizes VEGF-B activity has the potential to slow the rate of loss of renal function via pathways other than those impacted by either RAS or SGLT2 inhibition.

1.2 Information on CSL346

1.2.1 Overview

CSL346 is a novel humanized monoclonal antibody (immunoglobulin G 4) derived from the murine variant anti-VEGF-B antibody known as 2H10. CSL346 binds with high affinity to VEGF-B, which is expected to result in improvement of DKD with minimal off-target effects.

A detailed description of the chemistry, pharmacology, efficacy, and safety of CSL346 is provided in the Investigator's Brochure.

1.2.2 Nonclinical Evaluation

In CSL346 repeat-dose toxicity studies of up to a 6-month duration, there were no adverse events (AEs), including injection site reactions, observed up to the highest dose tested, 100 mg/kg, administered by intravenous (IV) or by subcutaneous (SC) injection. These data are supportive of administering repeat doses up to 16 mg/kg SC to subjects in clinical studies.

A detailed description of the nonclinical data available for CSL346 is provided in the Investigator's Brochure and Addendum.

1.2.3 Clinical Experience

The first in-human clinical study, CSL346_1001, a phase 1, randomized, double-blind, placebo-controlled single ascending dose study to evaluate the safety, tolerability, and pharmacokinetics (PK) of CSL346 in healthy Caucasian and Japanese adult subjects was completed in May 2019. Overall, no AEs of concern occurred following administration of single doses of CSL346 by an IV infusion (up to 20 mg/kg) or SC injection (up to 10 mg/kg) to 60 healthy volunteers, thus demonstrating safety and tolerability up to the maximum exposures achieved. The PK profile suggests dose proportionality and, as expected, is similar in Caucasian and Japanese subjects. The bioavailability after SC administration is estimated to be 61% in healthy volunteers. This study is supportive of continued development of CSL346, including administration of repeat doses of up to 16 mg/kg SC to subjects with DKD.

A detailed description of the safety and PK profile of CSL346 in healthy adult subjects is provided in the Investigator's Brochure.

1.3 Study Overview

This is a prospective, multicenter, randomized, double-blind, placebo-controlled, proof of concept study to investigate the efficacy, safety, tolerability, and PK of repeat doses of CSL346 in subjects with DKD and albuminuria receiving SOC treatment. Approximately 100 subjects will be randomized (1:1:2) to receive 8 mg/kg CSL346, 16 mg/kg CSL346, or placebo and participate for up to 34 weeks. [Section 3.1](#) provides a detailed overview of the study.

1.4 Potential Risks and Benefits

Benefits: Subjects in clinical studies generally cannot expect to receive direct benefit from treatments during participation, as clinical studies are designed to provide information about safety and efficacy of a new investigational product (IP). However, benefits may include the following:

1. Opportunity to contribute to the understanding of potential new treatment for DKD
2. Potential improvements in clinically important markers associated with DKD
3. Close medical evaluation and study-related medication and procedures

Risks: Risks identified to date in nonclinical and clinical investigations of CSL346 are nonserious injection site reactions with SC dosing. In the nonclinical toxicology studies with up to 6 months of dosing administered IV or by SC injection, no dose-limiting toxicity was seen up to the highest dose tested. There were no dose-limiting toxicities in the single ascending dose study in healthy volunteers, and the most common AEs reported across the 3 study parts were upper respiratory infection (Part A and Part B), headache (Part A and Part C), and injection site pain (Part C).

Administration of therapeutic proteins, including monoclonal antibodies such as CSL346, is associated with the risk of hypersensitivity and anaphylactic reactions, some of which can be serious and life-threatening. Appropriate precautions will be taken during CSL346 administration, with vigilant monitoring for potential anaphylactic reactions and treatment according to SOC. The initial administrations of CSL346 will be performed under medical supervision, and subjects will be advised to seek medical attention if delayed reactions occur after discharge from the site.

Additional safety monitoring and / or risk mitigation implemented for this study will include antidrug antibody development, weight gain, and congenital disorders.

Due to the potential for VEGF-B antagonism to modulate VEGF-A tone, adverse effects on renal and cardiac parameters known to occur in patients with metastatic cancer treated with anti-VEGF-A agents were also considered.

Subjects will have enhanced safety monitoring over the 4 weeks following their first exposure to blinded IP and before administration of the second SC dose at Week 4 (Visit 7). This includes frequent blood pressure (BP) monitoring at Visit 4 (Day 1) and study visits at Week 1 (Visit 5) and Week 2 (Visit 6).

An overview of identified and potential risks and planned risk mitigation in this phase 2a study is provided in Table 1.

Table 1 Risks and Risk Mitigation

Risk	Potential/ Identified	Source	Risk Mitigation
Injection site reactions	Identified	CSL346_1001 data on file	
 Assessment at study visits Guidance for managing local intolerance
Hypersensitivity / anaphylaxis and infusion reactions; antibody formation	Potential	Class effect of humanized proteins	
 Standard measures Measurement of baseline, mid-, and end of study anti-CSL346 antibody
Weight gain	Potential	Knock-out mouse model [Hagberg et al, 2010]	
 Monitor at study visits
Congenital disorders	Potential	Knock-out mouse model [Bellomo et al, 2000] Preclinical study in quails [Tomanek et al, 2006]	
 Inclusion / exclusion criteria Contraception requirements Pregnancy testing Nonclinical studies in later phases
Renal: acute reversible effect on GFR and / or chronic kidney injury	Potential	Theoretical risk due to VEGF-A modulation [Kamarzarian et al, 2018; Izzedine et al, 2010]	
 Inclusion / exclusion criteria Staged approach for enrollment of subjects with moderate renal impairment Frequent monitoring in first 4 weeks of treatment Measure SCr and evaluate albuminuria at each visit Guidance for managing increases in SCr and albuminuria

Risk	Potential/Identified	Source	Risk Mitigation
Cardiac: myocardial dysfunction with chronic dosing	Potential	Knock-out mouse model [Bellomo et al, 2000] Streptozotocin model [Lal et al, 2017] Theoretical risk due to VEGF-A modulation [Touyz et al, 2018]	
 Exclusion criteria, including baseline assessment of LVEF by ECHO Treatment with SOC Baseline and periodic ECG, BNP, and troponin levels Guidance for managing increases in troponin levels
Increased BP	Potential	Theoretical risk due to VEGF-A modulation [Touyz et al, 2018]	
 Exclusion criteria BP measurement Guidance for managing increases in BP

BP = blood pressure; BNP = b-type natriuretic peptide; ECG = electrocardiogram; ECHO = echocardiogram; GFR = glomerular filtration rate; LVEF = left ventricular ejection fraction; SCr = serum creatinine; SOC = standard of care; VEGF = vascular endothelial growth factor.

2 Study Objectives and Endpoints

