- E:** Vital signs include BP (systolic and diastolic), body temperature, and pulse rate. Blood pressure measurements should be taken in triplicate before all other assessments. Vital signs in general will be collected before any blood samples that are collected at the same time point. At Visit 2 (Day –21), BP will be the only vital sign collected. Instructions for measuring BP will be provided in the Manual of Operations. At Visit 4 (Day 1), vital sign measurements will be taken predose, at 30, 60, and 120 minutes (± 15 minutes) after the first IV dose of IP (before the first SC dose of IP) is administered, then at 30 and 60 minutes (± 15 minutes) after SC dosing.
- F:** Height will be measured at Screening only.

- G:** Electrocardiograms must be performed in triplicate before any blood samples that are collected at the same time point.
- H:** A local assessment of echocardiogram will be performed during Screening unless an echocardiogram was performed for non-study-related reasons within 3 months before Screening.
- I:** At Visit 2 (Day -21), a blood sample will be collected for determination of serum creatinine only.
- J:** A timed 24-hour urine sample will be collected to assess eligibility (ACR) at Screening (Baseline), and to measure CSL346 levels in urine at subsequent indicated visits.
- K:** Subjects will collect urine from their first morning void on 3 consecutive days (2 consecutive days for Visit 9) leading up to and including the morning of each indicated visit.
- L:** Morning midstream urine samples will be collected to evaluate exploratory biomarkers and will also be stored for future research analyses.
- M:** Specific instructions for administration of IP are provided in the IMP Handling Manual. At Visit 4 (Day 1), an initial loading dose of IP will be administered by IV, followed at least 2 hours (but no more than 6 hours) later by the subject's normal prescribed dose by SC infusion. Subsequent doses of IP will be administered by SC infusion.
- N:** Serial blood samples for PK will be collected at Visit 4 (Day 1) predose, at 30 (\pm 5 minutes), 60 (\pm 10 minutes), and 120 (\pm 10 minutes) minutes after the first IV dose of IP (before the first SC dose of IP) is administered, then after the final vital signs measurement. Single PK samples will also be collected at all subsequent visits (before treatment on SC dosing days).

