2.2 Secondary Objectives and Endpoints

2.2.1 Secondary Objectives

The secondary objectives of this study are as follows:

- To evaluate the safety and tolerability of CSL346 administered every 4 weeks for up to 12 weeks (4 doses) in subjects with DKD
- To evaluate the effect of CSL346 on serum creatinine (SCr) concentration and estimated glomerular filtration rate (eGFR) in subjects with DKD

3. To evaluate the effect of CSL346 on BP in subjects with DKD
4. To evaluate the PK of CSL346 in subjects with DKD
5. To evaluate the immunogenicity of CSL346 in subjects with DKD

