2.2.2 Secondary Endpoints

Secondary Objective	Endpoint	Summary Measure
1	Treatment-emergent adverse events, including adverse events of special interest (AESIs) from the time of first dose of the IP through End of Study (EOS)	Number and percentage of subjects overall, by severity, by relatedness, by seriousness, and by action (ie, IP discontinuation)
2	Observed value and change from Baseline in SCr and eGFR through EOS	Mean (SD)
3	Observed value and change from Baseline in systolic and diastolic blood pressure (SBP and DBP) through EOS	Mean (SD)
4	CSL346 serum PK: 
 • Maximum concentration (C_{max}) after IV loading dose • Time to reach C_{max} in serum (T_{max}) after IV loading dose • C_{max} after first SC dose • T_{max} in serum after first SC dose • Area under the concentration-time curve in first dosing interval ($AUC_{0-\tau}$) • Trough concentration (C_{trough}) after each dose 	Mean (SD), coefficient of variation (%CV) and geometric mean for all parameters except T_{max} ; Median (minimum, maximum) for T_{max}
5	Presence of anti-drug antibody at Week 4 (Visit 7), Week 8 (Visit 8), and Week 16 (Visit 10)	Number and percentage of subjects with positive result (with reciprocal titer)

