3.1.4 Follow-up Period

The Follow-up Period will continue for 12 weeks after the subject's last dose of IP to evaluate changes in safety, efficacy, PK, and PD parameters after stopping treatment.

Relevant unblinded data from all subjects participating in the study will be reviewed by the IDMC during regularly-scheduled safety reviews, as detailed in the IDMC Charter.

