Urinary ACR is an established renal surrogate biomarker in this patient population and has therefore been selected to evaluate efficacy for the primary objective [Coresh et al, 2019; Heerspink et al, 2019]. To minimize variability and optimize the ability to interpret the results, medications used for glycemic control and the treatment of DKD (eg, RAS inhibitors and SGLT2 inhibitors) must be stable before study enrollment. In addition, multiple, consecutive first morning void (FMV) urine collections at each time point will be used for ACR analysis [Kröpelin et al, 2015]. These samples will be collected at Baseline, periodically during the Treatment Period and at the end of the Treatment Period, and during the Follow-up Period. Based on results from studies conducted in standard animal DKD models, 12 weeks of dosing is highly likely to demonstrate ACR activity in a clinical study. The 12-week duration of the Follow-up Period was determined based on the extended half-life of CSL346 and enables characterization of the treatment effect while exposure declines.

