Differences in potency between the mouse 2H10 antibody and CSL346 were calculated using data from a cell-based assay of VEGF-R1 activity [Mould et al, 2005]. The half maximal inhibitory concentrations of 2H10 in the presence of mouse VEGF-B (20 nM) and of CSL346 in the presence of human VEGF-B (1.25 nM) were 3 nM and 0.18 nM, respectively. The ratio

of these values (16.7) was used to correct for the observed effective concentration of 2H10 in mice and predict a target C_{trough} of CSL346 in humans. With the 16.7 adjustment for potency, a target CSL346 C_{trough} of 11 $\mu\text{g}/\text{mL}$ was calculated. In a direct binding enzyme-linked immunosorbent assay, the half maximal effective concentration (EC_{50}) of 2H10 on 1 $\mu\text{g}/\text{mL}$ mouse VEGF-B was 3.21 nM and the EC_{50} of CSL346 on 1 $\mu\text{g}/\text{mL}$ human VEGF-B was 0.257 nM. When using the ratio of these values (12.5) to correct for the concentration in mice, a target C_{trough} of 14.4 $\mu\text{g}/\text{mL}$ was calculated. Selection of the doses was based on the 14.4 $\mu\text{g}/\text{mL}$ target C_{trough} , as the direct binding assay provides a more accurate measure.

Considering the prolonged half-life (approximately 30 days), up to 5 months of monthly administration would be required to reach steady state with SC administration. Therefore, a single loading dose will be administered by IV infusion on Day 1 (Visit 4), followed by an SC infusion on Day 1 (Visit 4) to reach approximate steady state CSL346 concentrations earlier in the Treatment Period. To maintain target serum concentrations, IP will be administered by SC infusion every 4 weeks thereafter.

[figure not shown]

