	
 • Hemoglobin • Hematocrit • Erythrocytes (RBC count) • Red blood cell indices: MCV, MCH, MCHC, RDW • Platelets • Differential (percentage and absolute): neutrophils, neutrophil band forms, lymphocytes, monocytes, eosinophils, basophils • Reticulocytes
Coagulation	
 • INR • PT • aPTT
Biochemistry	
 • Sodium • Potassium • Chloride • Bicarbonate • Carbon dioxide – total • Calcium • Urea nitrogen / BUN • Creatinine • Glucose • Protein – total • Albumin • Alkaline phosphatase • AST • LDH • GGT • Bilirubin – total • Direct bilirubin • CRP • Cholesterol – total • Triglycerides • HDL Cholesterol • LDL Cholesterol • Urate (uric acid) • Creatinine kinase
eGFR	
 • Glomerular filtration rate, estimated using the CKD-EPI equation.
Immunogenicity ^b	
 • Analysis for the presence of binding antibodies to CSL346

ALT = alanine aminotransferase; aPTT = activated partial thromboplastin time; AST = aspartate aminotransferase; beta-hCG = beta-human chorionic gonadotropin; BNP = b-type natriuretic peptide; BUN = blood urea nitrogen; CKD-EPI = Chronic Kidney Disease Epidemiology Collaboration; CRP = C reactive protein; ECG = electrocardiogram; ECHO = echocardiogram; GGT = gamma-glutamyl transferase; HBV = hepatitis B virus; hCG = human chorionic gonadotropin; HCV = hepatitis C virus; HDL = high density lipoprotein; INR = International Normalized Ratio; LDH = lactate dehydrogenase; LDL = low density lipoprotein; LVEF = left ventricular ejection fraction; MCH = mean corpuscular hemoglobin; MCHC = mean corpuscular haemoglobin concentration; MCV = mean corpuscular volume; PT = prothrombin time; QTcB = Bazett's correction formula; QTcF = Fridericia's correction formula; RBC = red blood cell; RDW = erythrocyte distribution width; WBC = white blood cell.

^a A conventional (not high-sensitivity) troponin-I assay specific for the cardiac isoform of troponin-I will be performed by the central laboratory.

^b Immunogenicity will be assessed via a tiered approach using screening, specificity, and titration assays.

Laboratory Parameters

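### Protocol Table 1 promises an end-of-study anti-CSL346 antibody measurement, but no antibody sample is scheduled after Week 16

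*Protocol*

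**What the plan says.** Protocol 1.4, Table 1 gives "Measurement of baseline, mid-, and end of study anti-CSL346 antibody" as part of the mitigation for hypersensitivity, infusion reactions and antibody formation. Secondary objective 5 (protocol 2.2.1) reads: "To evaluate the immunogenicity of CSL346 in subjects with DKD".

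The operative texts give a different set of times:

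- The immunogenicity row of the Schedule of Assessments (protocol, repeated in SAP 16.8) is marked at Visit 4 (Day 1), Visit 7 (Week 4), Visit 8 (Week 8) and Visit 10 (Week 16). The EOS cell is empty.
- The visit lists in protocol 8.6.4 and 8.6.5 agree. At EOS (8.6.5.2: Week 24, Day 169) blood is drawn for hematology and biochemistry, troponin-I and BNP, HbA1c and PK, but not for antibodies.
- Secondary endpoint 5 (protocol 2.2.2, SAP Table 1) and the analysis in SAP 11.4.1 name Weeks 4, 8 and 16 only.

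On the purpose of follow-up, protocol 3.1.4 says it is "to evaluate changes in safety, efficacy, PK, and PD parameters after stopping treatment". Protocol 3.3.1 adds: "The 12-week duration of the Follow-up Period was determined based on the extended half-life of CSL346". Table 6 in protocol 8.1.1 classes immunogenicity as a safety assessment, with the footnote "Immunogenicity will be assessed via a tiered approach using screening, specificity, and titration assays".

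**The concern.** A monitoring measure offered in the risk table is not carried out. Reading the lower-case phrase in Table 1 as Week 16 is hard to sustain: the protocol uses End of Study for Week 24 throughout and treats Week 16 as a separate follow-up visit.

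The missing sample also has content. Follow-up was sized to the drug's long half-life, so that the subject can be observed while exposure falls, yet antibody sampling stops one third of the way through it. Two things are lost:

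- Antibodies first appearing after Week 16 go unseen, so objective 5 is answered with no estimate of, and no upper bound on, late antibody formation.
- An unexpectedly low EOS concentration could not be checked against antibody status at the same visit. Stored samples do not fill the gap, because the biomarker blood row also ends at Week 16.

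**Working it through.** The plan gives no figure to reproduce, so the check is a mapping of the schedule followed by simple arithmetic.

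**1. Antibody samples against PK samples** (Schedule of Assessments; protocol 8.6)

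| Visit | Study day | Serum PK | Antibody |
|---|---|---|---|
| 4 | 1 | yes | yes |
| 5 (Week 1) | 8 | yes | no |
| 6 (Week 2) | 15 | yes | no |
| 7 (Week 4) | 29 | yes | yes |
| 8 (Week 8) | 57 | yes | yes |
| 9 (Week 12, last dose) | 85 | yes | no |
| 10 (Week 16) | 113 | yes | yes |
| EOS (Week 24) | 169 | yes | no |

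Of the 7 PK visits after Day 1, 3 have a concurrent antibody sample. EOS has none.

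**2. Share of follow-up after the last antibody sample**

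- Last dose to Week 16: 113 − 85 = 28 days.
- Last dose to EOS: 169 − 85 = 84 days.
- Not covered: 84 − 28 = 56 days; 56/84 = 67%.
- Visit windows (±5, ±7 and ±7 days) put the last dose on Days 80–90, Week 16 on Days 106–120 and EOS on Days 162–176. The extremes are (162 − 120)/(162 − 80) = 42/82 = 51% and (176 − 106)/(176 − 90) = 70/86 = 81%.

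**3. Drug remaining** (half-life about 30 days, protocol 3.3.2; simple exponential decline assumed)

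- Week 16 is 28/30 = 0.93 half-lives after the last dose; EOS is 84/30 = 2.8.
- EOS level relative to Week 16: 2^(−56/30) = 0.274, about 27%.
- Across the visit windows: 2^(−42/30) = 0.379 to 2^(−70/30) = 0.198.
- For an assumed half-life of 25 or 35 days: 0.212 or 0.330.

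**4. What one EOS sample could show**

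The documents give no antibody incidence, so the late-onset rates p = 2% and 5% are illustrative. The number of CSL346 subjects at EOS is assumed to be 50 × (1 − 0.06) = 47, with 40 to 50 as a range. Every true positive is assumed to be detected.

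Probability of at least one late-onset positive is 1 − (1 − p)^n. The one-sided 95% upper limit when none of n is positive is 1 − 0.05^(1/n).

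| n | p = 2% | p = 5% | Upper limit if none positive |
|---|---|---|---|
| 40 | 0.554 | 0.871 | 7.2% |
| 47 | 0.613 | 0.910 | 6.2% |
| 50 | 0.636 | 0.923 | 5.8% |

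Under the present schedule the scheduled samples have probability zero of showing a late-onset positive, and no limit can be stated.

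**The case against.** The best counter-argument is that only one phrase in an overview table is out of step. Sites follow the schedule and visit lists, which agree with each other and with endpoint 5, so rewording Table 1 to the four actual times would remove the contradiction without a new sample. On this view an EOS sample is a design preference in a phase 2a study: endpoint 5 is delivered as defined, one off-treatment sample is already taken, and dosing ends on Day 85, so a Week 24 result could not prevent a reaction in this trial. Protocol 3.3.1 speaks of the treatment effect during washout and does not mention antibodies. Unscheduled safety samples are allowed (8.1, 8.3.1).

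Much of this is factually right and limits the point. It does not remove it. Rewording makes the text consistent but leaves late antibody formation unmeasured. Protocol 3.1.4 gives follow-up a safety purpose, and immunogenicity is classed as a safety assessment. Samples taken on clinical suspicion are not systematic detection.

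Three criticisms of the numbers deserve weight:

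- The 2% and 5% rates have no source in the documents.
- The figure of 47 comes from the 94 target completers, who are defined at Week 16 and not at EOS. Randomizing up to 124 aims at those same 94 completers.
- Drug could interfere with the antibody assay at EOS as well as earlier. Protocol 3.3.2 predicts that 59% of 16 mg/kg subjects still exceed 14.4 µg/mL at Week 24, which is 14.4/0.08 = 180 times the 80 ng/mL serum quantification limit for CSL346 in SAP 12.1. The documents do not state the assay's drug tolerance, so this is a possibility only. EOS is nevertheless when drug is lowest after dosing.

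**Conclusion.** The concern holds. Table 1 promises an end-of-study antibody measurement that no schedule, visit list, endpoint or analysis provides. The gap is the last 56 of 84 follow-up days (67%; 51% to 81% across the visit windows), during which drug falls to about 27% of its Week 16 level. This rests on the stated half-life of about 30 days and simple exponential decline.

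What is lost is information on objective 5: an upper limit of about 6.2% for late-onset antibodies (5.8% to 7.2% for 50 down to 40 subjects) if none were positive, and a fair chance of seeing a 2% to 5% rate. Both figures assume the stated numbers at EOS and full assay sensitivity. The primary analysis, power, alpha, the stopping rules and endpoint 5 as written are untouched. The change is worth making but is not critical to the trial's main conclusion.

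**What to change.** Add an immunogenicity sample at EOS, taken from the existing blood draw:

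- Mark it in the Schedule of Assessments (protocol and SAP 16.8) and in protocol 8.6.5.2.
- Add Week 24 to secondary endpoint 5 (synopsis, 2.2.2, SAP Table 1) and to SAP 11.4.1. The any-time comparison in protocol 10.3.7 would then include the result without rewording.
- Report subjects first positive at Week 24 separately, so that the late-onset estimate or limit can be read off.

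The cost is one more sample per subject through the tiered assay: 100 to 124 samples if everyone randomized attends, with the specificity and titration steps only for those that screen positive. No visit or venepuncture is added. It needs an IRB/IEC-approved amendment (13.3) and, where participation is affected, an amended consent form and re-consent (12.3).

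If the sponsor decides against the sample, Table 1 should at least be corrected to Day 1 and Weeks 4, 8 and 16. That settles the wording but not the gap.
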